6.6.2. Binary Endpoints

The non-responder imputation (NRI) approach will apply to both part A and part B binary endpoints, unless otherwise specified.

Subjects who are considered as treatment failures, as defined in [Section 5.8](#), will be considered as non-responders for all the visits post treatment failure visit.

Subjects who discontinued treatment will be classified as non-responders for all the visits following treatment discontinuation. Intermittent (non-monotonic) missing data will be imputed based on last observation carried forward (LOCF) approach. Subjects who completed treatment but had a missing score at primary timepoint (Week 24 of Part A or Week 12, 16 of Part B) will also be classified as non-responder for that timepoint, except for subjects from PV1 Part B who completed treatment up to week 12. These subjects will have the binary response derived based on the imputation of week 16 data under MAR assumption as discussed in [Section 6.6.1](#).

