- Nature, severity, relationship to study treatment, and incidence of adverse events (AEs) and serious adverse events (SAEs)
- Change from baseline in standard laboratory parameters, vital signs and electrocardiogram (ECG) results
- Immunogenicity (antibodies to BIIB059)
- Absolute and percent change from baseline over time in immunoglobulin levels and vaccine-related immunoglobulin titers

Additional study objectives are listed in Section 6.

Study Design:

2-part, randomized, double-blind, parallel group, placebo-controlled study

Study Location:

The study will be conducted at approximately 130 centers in the United States, Europe, Latin America, and Asia.

Number of Planned Subjects:

Part A:

The maximum number of subjects in Part A is approximately 190 subjects. Of these 190 subjects, approximately 100 subjects will be enrolled under protocol version 2 or subsequent versions. If the study is not stopped for futility at the interim analysis (IA 1), then up to 70 additional subjects may be added (up to a total of approximately 170 subjects under protocol version 2 or subsequent versions). Subjects enrolled under protocol version 1 will remain on their original treatment assignment (up to a total of approximately 20 subjects).

CONFIDENTIAL

The information contained herein may not be used, disclosed, or published without the written consent of Biogen MA Inc.

Part B:

The maximum number of subjects in Part B is approximately 130 subjects. Of these 130 subjects, approximately 100 subjects will be enrolled under protocol version 2 or subsequent versions. Subjects enrolled under protocol version 1 will remain on their original treatment assignment (up to a total of approximately 30 subjects).

An interim analysis (IA 1) for futility of Part B and possible expansion of Part A will be performed. IA 1 will be performed after approximately 45% of Part B subjects under protocol version 2 or subsequent versions have completed their Week 12 Treatment Period visit. At the time of this IA, it is estimated that over 50% of subjects in Part A will have completed their Week 12 Treatment Period visit. Following the IA, up to an additional 70 subjects may be enrolled in Part A and the BIIB059 dose may be adjusted. Details are provided in Section [16.7.1](#).

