6.1.2. Part B Efficacy Analyses Considerations

Continuous endpoint

All Part B continuous efficacy endpoints will be analyzed using the following described method, unless otherwise specified.

A Mixed Effect Model Repeat Measurement (MMRM) model will be used as the primary method to analyze endpoint of interest using treatment group, study visit (week 2, 4, 8, 12, 16),

CONFIDENTIAL

The information contained herein may not be used, disclosed, or published without the written consent of Biogen MA Inc.

 Biogen	Statistical Analysis Plan 230LE201	<V 2.0>
--	---	----------------------

study visit-by-treatment interaction, DLE (Yes/No), CLASI-A score (≤ 10 vs. > 10), baseline value of the endpoint and baseline-by-visit interaction as fixed effect covariates. An unstructured covariance matrix will be used to model the within-patient variance-covariance errors. If the unstructured covariance structure matrix results in a lack of convergence, the heterogeneous Toeplitz covariance structure followed by the heterogeneous first-order autoregressive covariance structure will be used. The Kenward-Roger approximation will be used to estimate the denominator degrees of freedom. The primary treatment comparison between each BIIB059 treated group and placebo will be at the end of the Week 16. Handling of missing data and data from treatment failures subjects is provided in [Section 6.6](#).

Binary endpoint

The binary endpoints will be analyzed using logistic regression with covariates of treatment and DLE (Yes/No) and CLASI-A score (≤ 10 vs. > 10). For binary endpoints dichotomized from a continuous endpoint (such as PGA VAS < 1 point increase, the baseline of the continuous endpoint will be added to the above covariates list. The odds ratio, its 95% CI and the p-value for each BIIB059 dose compared to placebo will be presented. Early discontinuation(s) and/or treatment failures will be handled using non-responder imputation approach as discussed in [Section 6.6](#).

[REDACTED]

[REDACTED]

[REDACTED]

[REDACTED]

[REDACTED]

[REDACTED]

Censoring rules: Subjects who do not experience an event by Week 16 or early termination will be censored at the date of last assessment during the treatment period. The start date for calculation of day to censor or event will be the date of first dose.

CONFIDENTIAL

The information contained herein may not be used, disclosed, or published without the written consent of Biogen MA Inc.

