6.6.1. Continuous Endpoints

The primary approach described below will apply to both part A and part B continuous endpoints, unless otherwise specified. The sensitivity approach will be applied to the primary endpoints.

Primary approach

For subjects who are considered as treatment failures, as defined in [Section 5.8](#), the worse observation of the baseline and the last observation before treatment failure carried forward will be used as the primary method to impute values for all the visits post treatment failure visit. Under this approach, subject's post treatment failure data will be censored and then imputed with the subject's worst case non-missing data prior to treatment failure.

Data after treatment discontinuation will be censored and treated as missing data. For all other monotone and non-monotone missing data, including missingness post treatment discontinuation, mixed-effects model repeated measures (MMRM) model based approach will be used as the primary approach. MMRM assumes data is missing at random (MAR).

A few subjects from PV1 part B might have completed treatment up to week 12 but could not reconsent to PV2 and therefore will have missing week 16 data. These subjects will have week 16 data imputed using predicted value from the MMRM model.

Sensitivity analyses approach

For subjects who are considered as treatment failures, as defined in [Section 5.8](#), the worse observation of the baseline and the last observation before treatment failure carried forward will be used to impute values for all the visits post treatment failure visit. Under this approach, subject's post treatment failure data will be censored and then imputed with the subject's worse case between the baseline and the last non-missing data prior to treatment failure.

CONFIDENTIAL

The information contained herein may not be used, disclosed, or published without the written consent of Biogen MA Inc.

 Biogen	Statistical Analysis Plan 230LE201	<V 2.0>
--	---	----------------------

For all the other missing data, including missingness post treatment discontinuation, reference-based Multiple Imputation (MI) approach will be used to consider a missing not at random (MNAR) mechanism for monotonic missing data. Imputed values of subjects in the BIIB059 group will be based on the Placebo group. This approach assumes no sustained benefit of BIIB059 after discontinuation of study treatment and limits post-discontinuation effects to that of placebo.

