Intermittent (non-monotonic) missing data will be imputed based on the MAR assumption and with an imputation model using Markov chain Monte Carlo (MCMC) method within each treatment group. The imputation models will include baseline value and the values at each post-baseline week for endpoint of interest. The MCMC method in the MI procedure in SAS will be used with a single chain, with a burn-in of 1000, and a thinning of 100 and non-informative priors for all parameters.

The remaining, monotonic missing data for all subjects who discontinue study treatment early will be imputed using sequential regression MI model estimated based on data from the placebo group only. Each sequential regression model (i.e., for imputation of values at a given week) will include terms for baseline score, the stratification factors, and all the continuous endpoint scores. Missing values at a given week in placebo and BIIB059 groups will be imputed from the same imputation model. No rounding or range restrictions will be applied to imputed continuous values.

200 imputations will be performed. Each of the 200 imputed datasets will be analyzed using the following method.

Results from analysis of each imputed dataset, i.e., least square (LS) mean differences from placebo and their SEs, will be combined using Rubin's method [\[Rubin 1987\]](#) as implemented in the SAS MIANALYZE procedure to produce a pooled LS mean estimate of treatment difference, its 95% CI, and a pooled p-value. A p-value will only be presented for the primary

CONFIDENTIAL

The information contained herein may not be used, disclosed, or published without the written consent of Biogen MA Inc.

comparison at primary timepoint. The LS means of change from baseline to each post-baseline week will be plotted by treatment group.

A figure of the change from baseline to the primary timepoint will be presented; for data imputed using the MI methodology described above the least square mean of the 200 imputed values will be used.

A few subjects from PV1 part B might have completed treatment up to week 12 but could not reconsent to PV2 and therefore will have missing week 16 data. These subjects' week 16 data will be considered MAR and imputed using MMRM.

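### Week 16 responder status for Version 1 Part B subjects who did not reconsent comes from thresholding what reads as a single MMRM prediction, analysed as if observed; the effect is small for a few subjects and larger towards 30

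*SAP*

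**What the plan says.** SAP 6.6.1 identifies the group: "A few subjects from PV1 part B might have completed treatment up to week 12 but could not reconsent to PV2", so their Week 16 data are missing. Under the primary approach, "These subjects will have week 16 data imputed using predicted value from the MMRM model". Under the sensitivity approach they are again kept apart from the reference-based imputation; their "week 16 data will be considered MAR and imputed using MMRM".

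SAP 6.6.2 classes other subjects with a missing Week 16 score as non-responders, but exempts this group: "These subjects will have the binary response derived based on the imputation of week 16 data under MAR assumption", with a cross-reference to 6.6.1. The endpoints concerned are CLASI-50, the 4-point and the 7-point reduction in CLASI-A at Week 16 (SAP 6.3.1 to 6.3.3).

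The analysis model is in SAP 6.1.2: "The binary endpoints will be analyzed using logistic regression with covariates of treatment and DLE (Yes/No") and CLASI-A stratum. No pooling over imputed datasets is described for it. Multiple imputation appears only in the sensitivity approach of 6.6.1 ("200 imputations will be performed"), whose scope is limited: "The sensitivity approach will be applied to the primary endpoints".

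On numbers, the Protocol synopsis gives a ceiling for Part B: "Subjects enrolled under protocol version 1 will remain on their original treatment assignment (up to a total of approximately 30 subjects"). SAP 2.1.2 states that Version 1 Part B randomised 450 mg or placebo 2:1 and that reconsent was possible. SAP 3.1 pools all Part B data by treatment group across protocol versions.

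**The concern.** A model prediction is an expected value, whether it is conditional on the subject's earlier visits or a marginal fitted mean. It has less spread than a real Week 16 score. For a continuous mean this is chiefly a variance problem. For a responder rate it is also a bias, because a non-linear cut is applied to a value whose spread has been removed. MAR justifies the imputation model; it does not justify replacing a distribution by its mean before thresholding.

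The derived yes/no then enters the logistic model with the same weight as an observed response, so its uncertainty is not counted. Because these subjects sit only in the 450 mg and placebo arms, and unequally, the distortion does not in general cancel in that comparison. The 450 mg versus placebo odds ratios and p-values for three named Week 16 secondary endpoints, each tested at two-sided 0.05 (SAP 6.1), are at stake. SAP 6.7 repeats the same methods in the per-protocol population.

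**Working it through.** **Inputs.** From the documents: SD 30 for Week 16 percent change (SAP 11); cut-off -50% for CLASI-50 (SAP 6.3.1); 25 subjects per arm (SAP 11); ratio 2:1; at most about 30 subjects affected. Assumed: normality; mean changes -45 (450 mg) and -15 (placebo), a gap close to but not equal to the SAP's 27.5; correlation ρ between prediction and true score of 0.7 to 0.8; 25 observed subjects per arm with no dropout.

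**The plan's own figure.** The plan gives no figure for this rule. The one stated figure that uses the same SD is the Part B power of about 90%. It reproduces: with 20 per arm after dropout, the five candidate shapes give 0.892 to 0.942, mean 0.920. The SD is therefore a fair base.

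**Step 1: rates among affected subjects.** True rate = Φ((-50 - mean)/30). Thresholded-prediction rate = Φ((-50 - mean)/(30ρ)).

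- True: Φ(-5/30) = 43.4% and Φ(-35/30) = 12.2%; OR = (0.434/0.566)/(0.122/0.878) = 5.5.
- ρ = 0.7: Φ(-5/21) = 40.6% and Φ(-35/21) = 4.8%.
- ρ = 0.8: Φ(-5/24) = 41.7% and Φ(-35/24) = 7.2%.

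**Step 2: the comparison that is reported.** Pool with 25 observed subjects per arm: rate = (25 × true + n × predicted)/(25 + n). Example, 4 + 2 subjects at ρ = 0.7: 450 mg (25 × 0.434 + 4 × 0.406)/29 = 43.0%; placebo (25 × 0.122 + 2 × 0.048)/27 = 11.6%; OR 5.7.

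| Affected (450 mg + placebo) | Overall OR, ρ 0.8 to 0.7 |
|---|---|
| none | 5.5 |
| 2 + 1 | 5.6 |
| 4 + 2 | 5.7 |
| 10 + 5 | 5.9 to 6.0 |
| 20 + 10 | 6.2 to 6.5 |

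At ρ = 0.5 the last two rows become 6.2 and 6.9.

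**Step 3: direction.** The same formula at other assumed means:

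| Mean change | True rate | Predicted-value rate, ρ 0.5 | ρ 0.8 |
|---|---|---|---|
| -20 | 15.9% | 2.3% | 10.6% |
| -47.5 | 46.7% | 43.4% | 46% |
| -57.5 | 59.9% | 69.1% | 62.3% |

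If the prediction were the marginal mean (ρ = 0), these rates would be 0%, 0% and 100%. With equal means of -20 in both arms, ρ = 0.5 and 30 affected, the simulated rate difference is -0.021 instead of 0. The rule can therefore also work against 450 mg.

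**Step 4: precision.** Simulated difference in response rates, 25 observed per arm, ρ 0.5 or 0.8, mean pairs -20/-47.5, -30/-57.5 and -20/-20:

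- Coverage of the 95% interval with a single prediction: 89-94% for 6 affected, 85-93% for 15, 72-92% for 30.
- Worst bias: +0.08 (30 affected, ρ = 0.5, means -30/-57.5).
- Standard error 0.090 against an actual spread of 0.129 (30 affected, ρ = 0.5, means -20/-47.5).
- Random draws combined with Rubin's rules: essentially unbiased, coverage 94-97%.

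On the log odds ratio scale, with the Step 1 means and ρ 0.7 to 0.8 (unadjusted, 0.5 added to each cell), the harm is milder. Bias is +0.02 with 3 affected, +0.03 with 6 (standard error about 0.73), +0.07 to +0.10 with 15 and +0.12 to +0.16 with 30. Coverage stays at about 95-97%.

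**The case against.** The strongest reply is scale. The SAP expects only a few such subjects and says they might arise. The 20 + 10 case needs every Version 1 subject to complete Week 12 and none to reconsent, although reconsent was allowed. At 3 to 6 subjects the bias in the log odds ratio is a small fraction of its standard error. The endpoints are secondary and not adjusted for multiplicity, and the same three responses are analysed at Week 12, where these subjects have data. All of this stands and sets the priority.

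The second reply is textual: 6.6.2 speaks only of imputation under MAR, which could cover random draws. That is possible. But the section it refers to says predicted value, and no draws, number of imputations or pooling step are given for binary endpoints. The text also leaves open whether the prediction is subject-conditional or marginal. A single prediction is the natural reading, not a stated fact.

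Stronger readings that a reader might infer, and which the documents do not support:

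- That the odds ratio is inflated to 9-14. That range follows from the Step 1 rates (41.7% vs 7.2%, and 40.6% vs 4.8%), but it contrasts imputed subjects only, which the SAP never reports.
- That the rule always favours 450 mg. The direction depends on arm means that the documents do not give.
- That interval coverage generally collapses. The 72% figure is the worst case, for a rate difference with 30 affected; the SAP reports an odds ratio.
- That the primary MCP-Mod result is compromised. This binary rule does not enter it.

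**Conclusion.** The point holds as a minor flaw in specification. As written, the rule misclassifies some Week 16 responders in the 450 mg and placebo arms and treats imputed outcomes as observed. With a few affected subjects the consequence is negligible to small (overall CLASI-50 odds ratio 5.5 to 5.6-5.7). It grows as the number approaches the ceiling of about 30 (6.2-6.5). These sizes rest on assumed means, correlation and normality; only the SD, cut-off, arm size, ratio and ceiling come from the documents. A weaker correlation, or a marginal rather than subject-conditional prediction, would make the effect larger.

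A related gap needs settling at the same time. SAP 6.2.1 fits the MMRM to percent change, and the SAP does not say how the 4-point and 7-point responses are obtained from its prediction. No calculation was made for those two cut-offs.

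**What to change.** In SAP 6.6.2, replace the exception for these subjects with the following:

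- Draw Week 16 CLASI-A values under MAR within treatment group, conditional on baseline and earlier visits and with residual variance, for example in 200 imputations.
- Use the within-arm MCMC model that 6.6.1 already specifies for intermittent missing data, and state that it is extended to this group. The sequential regression step for monotone missing data should not be reused: it is estimated from placebo only and would impose placebo behaviour on 450 mg subjects who completed their planned treatment.
- In each dataset derive CLASI-50, the 4-point and the 7-point response from the drawn score, fit the logistic model, and combine the log odds ratios with Rubin's rules. Drawing the score itself also closes the gap on the point-reduction endpoints.
- As a sensitivity analysis, exclude Version 1 subjects who did not reconsent from the Week 16 binary analyses.
- Report the number of affected subjects by arm.

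The cost is a little programming and slightly wider intervals. The rule should be settled before unblinding.

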6.6.3. Missing Data in Subcomponents

For missingness in subcomponents of efficacy instruments, such as subcomponents in joint counts, CLASI, SLEDAI-2K, BILAG and etc., imputation will be performed for the missing

CONFIDENTIAL

The information contained herein may not be used, disclosed, or published without the written consent of Biogen MA Inc.

subcomponents first. If there are $\leq 50\%$ subcomponents missing at one visit, missing data of subcomponents will be imputed based on LOCF approach. If there are $> 50\%$ subcomponents missing at one visit, this visit will be considered missing and the missingness will be imputed at the component level based on approaches described in [Section 6.6.1](#) and [Section 6.6.2](#). The same rule will apply to subcomponents of each component of the composite endpoints (e.g.: SRI-4). For endpoints with more than 1 level of subcomponents, where the overall score consists of multiple domains and each domain consists of multiple subcomponents, this rule will be applied to subcomponents under each domain.

[REDACTED]

6.7. Per-Protocol Analyses

Part A

The primary efficacy endpoint, active joint count, and the following secondary efficacy endpoints will be analyzed for the per-protocol population using the same analysis methods as for the MITT population.

- Percent change in CLASI-A score from Baseline
- SRI-4 response

CONFIDENTIAL

The information contained herein may not be used, disclosed, or published without the written consent of Biogen MA Inc.

Part B

The primary efficacy endpoint, percent change from baseline in CLASI-A score, and the following secondary efficacy endpoints will be analyzed for the per-protocol population using the same analysis methods as for the MITT population.

- Proportion of subjects with a CLASI-50 response, defined as a 50% improvement from baseline in CLASI-A score by visit
- Proportion of subjects with a ≥ 4 -point reduction in CLASI-A score by visit
- Proportion of subjects with a ≥ 7 -point reduction in CLASI-A score by visit

[REDACTED] [REDACTED]

A large black rectangular redaction box covers the majority of the page content, starting below the header and ending above the footer.

© 2013 Pearson Education, Inc.

© 2013 Pearson Education, Inc. All Rights Reserved. May not be copied, scanned, or duplicated, in whole or in part. Due to electronic rights, some third party content may be suppressed from the eBook and/or eChapter(s). Editorial review has determined that any suppressed content does not materially affect the overall learning experience. Pearson Education, Inc. reserves the right to remove additional content at any time if subsequent rights restrictions require it.

© 2013 Pearson Education, Inc. All Rights Reserved. May not be copied, scanned, or duplicated, in whole or in part. Due to electronic rights, some third party content may be suppressed from the eBook and/or eChapter(s). Editorial review has determined that any suppressed content does not materially affect the overall learning experience. Pearson Education, Inc. reserves the right to remove additional content at any time if subsequent rights restrictions require it.

© 2013 Pearson Education, Inc.

© 2013 Pearson Education, Inc. All Rights Reserved. May not be copied, scanned, or duplicated, in whole or in part. Due to electronic rights, some third party content may be suppressed from the eBook and/or eChapter(s). Editorial review has determined that any suppressed content does not materially affect the overall learning experience. Pearson Education, Inc. reserves the right to remove additional content at any time if subsequent rights restrictions require it.

For more information, contact the Office of the Vice President for Research and Economic Development at [contact] or [contact].

Digitized by [contact]

1100 1100 1100 1100

1 [REDACTED]

1 | Page

1 | Page

A thick black horizontal bar with a vertical black bar on the far left.

Digitized by [contact]

Digitized by [contact]

A series of horizontal black bars of varying lengths and positions, likely representing data points or markers in a sequence. The bars are arranged in several groups: a top group of four bars (the first being very long), a middle group of ten bars (the first being very short), and a bottom group of five bars (the first being very long). The bars are set against a white background.

CONFIDENTIAL

The information contained herein may not be used, disclosed, or published without the written consent of Biogen MA Inc.

[REDACTED]

[REDACTED]

[REDACTED]

[REDACTED]

[REDACTED]

[REDACTED]

[REDACTED]

[REDACTED]

